The primary objectives of this trial will be to compare rates of self-reported, symptomatic volume GOR and objectively measured rates of volume GOR using scintigraphy, between the two study groups. This will be a superiority trial, with the hypothesis being that palliative oesophageal anti-reflux self-expanding fully covered metal stents significantly reduce volume GOR compared to conventional oesophageal self-expanding fully covered metal stents.

Secondary Objectives

Secondary objectives will be to compare outcomes, including rates of dysphagia, cough, pain, stentrelated complications, subsequent complications and patient survival at the end of the study period. A further objective will be to compare the self-reported GOR questionnaire (GerdQ) outcomes to the objectively measured oesophageal scintigraphy measurements.

METHODS

Trial Design

This study will be a prospective randomised controlled trial comparing anti-reflux oesophageal stents to conventional oesophageal stents. Randomisation to an anti-reflux stent versus a conventional stent will be done prior to stent placement and the patient will remain blinded to the type of stent placed. Although the authors will not be blinded to the stent type, as the stents are easily distinguished from each other at the time of endoscopy, the Clinical Coordinator who will be doing the follow-up will be blinded to this. This study will be performed following the CONSORT 2010 checklist of information for randomised trials ²².

Once the study is approved by the University of Cape Town's Human Research Ethics Committee, approval for the study will also be obtained from Groote Schuur Hospital. The trial will then be registered with the South African National Clinical Trials Register (SANCTR) and at clinicaltrials.gov. Both stents being compared in this trial are already approved by the South African Health Products

Regulatory Authority (SAHPRA), and as they form part of standard of care, application to SAHPRA will not be necessary.

Participants

Eligibility criteria for trial participants:

Inclusion Criteria (all criteria must be met):

- Adult patients 18 years of age or older
- Informed consent obtained from the patient after oral and written explanation of the trial
- Histologically confirmed malignancy of the distal oesophagus or OGJ
- Obstructive or irresectable malignancy due to metastases, local tumour infiltration or poor performance status

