Patients with palliative oesophageal cancer are in most instances frail and have a significantly limited life expectancy. It is thus imperative upon discharge, that further research-related follow-up should not inconvenience the patient nor have a negative effect on their quality of life. Furthermore, many of the patients treated at GSH have limited financial means to afford repeated follow-ups at the hospital. For these reasons, subsequent follow-up after discharge, will be done telephonically. Patients will be phoned at 1, 2, 4 and 8 weeks post stent insertion and will be asked about any symptoms related to the stent insertion, and have an assessment of symptomatic GOR using the GerdQ questionnaire ⁸, dysphagia, cough and pain levels at each telephonic follow-up. Telephonic follow-up of these patients will be done by the Clinical Coordinator, who is blinded to which type of stent the patient has received.

All patients will also be referred to the GSH Palliative Care Team. With any symptom reported by a patient or family member that is deemed to possibly require further intervention or treatment, the patient will be requested to return for an evaluation or appropriately managed according to the Palliative Care Distress Algorithm (Appendix 1). All complications will be managed as per standard treatment routinely employed for such a complication at GSH. Any such complications will be documented.

OUTCOME MEASURES

Primary Outcome Measure

The primary outcome will be patient-reported rates of symptomatic volume GOR and objectively measured volume GOR in both study groups. Patient-reported symptomatic volume GOR will be assessed using the validated GerdQ questionnaire (Appendix 2)⁸. This questionnaire has been chosen has it is simple, easy to understand and includes only 6 questions, which are all reflux-related. This questionnaire will be administered to the patient prior to the procedure, to establish a baseline. It will then subsequently be telephonically administered at the scheduled telephonic follow-ups at weeks 1, 2, 4 and 8. The GerdQ questionnaire enables the patient to provide a score at each follow-up interaction which can then be documented and the mean scores between the two groups can then be compared.

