GOR will also be objectively measured on day 1 post stent insertion using scintigraphy. The proposed protocol for scintigraphy is described in Appendix 3. This modality has been chosen as its accuracy compares favourably to pH monitoring⁹, but is much less invasive. It requires the patient to swallow a meal of soft, runny porridge and then undergo imaging. pH monitoring is invasive, requiring the insertion of an uncomfortable nasal probe which stays in-situ for 24 hours, increasing discomfort for the patient but also increasing the hospital stay by a further 24 hours. It is thus deemed inappropriate in this setting.

Secondary Outcome Measures

The secondary outcomes that will be assessed will include immediate technical success rate and any complications related to the stent insertion, subsequent stent-related complications, patient-reported dysphagia score prior to stent insertion, on day 1 post-insertion and then at each of the scheduled telephonic follow-ups and lastly, patient survival at 2 months post stent insertion. Dysphagia assessment will be done using the modified dysphagia scale first published by Mellow and Pinkas and validated for assessing dysphagia after metal stent insertion for oesophageal cancer (Appendix 4)²³. Furthermore, an assessment of the patient's pain level and whether they are coughing will also be documented, using validated pain²⁴ and cough scores²⁵ and pain (Appendix 5 & 6).

Data Collection

The following data parameters will be collected:

- Age
- Gender
- Performance status25 and BMI of the patient at time of stent placement
- Histological type of malignancy (e.g. adenocarcinoma, squamous cell carcinoma or other)
- Reason for inoperability: metastases, locally advanced or poor performance status
- Position of oesophageal malignant stricture (endoscopic measurement in centimetres from the incisors)
- Patient-reported degree of dysphagia prior to stenting
- Patient-reported GerdQ score pre-stenting
- Stent characteristics: anti-reflux vs conventional, length, diameter and brand name of stent
- Immediate technical success rate
- Immediate stent insertion complications:
 - o Bleeding
 - Perforation
 - o Other

- Subsequent stent-related complications during the follow-up period:
 - o Bleeding
 - Perforation
 - Migration
 - Stent occlusion and cause thereof
 - \circ Other
- Quantitative assessment of volume reflux as per scintigraphy (on day 1)
- GerdQ score at follow-up at week 1, 2, 4 and 8

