 - Series: Name the acquisition series according to the time of imaging post last +swallow! The first image will be named the exact time after last swallow (e.g. STATIC 3min), and the rest of the images will be named according to the imaging protocol! (STATIC 0min [i.e. immediately after last swallow], 1hr, 2hr, 3hr, and 4hr)
 - **Zoom:** 1.0
 - Camera Preset: Tc99m-NMG
 - Detectors: Both Detectors
 - Time per view: 60 sec
 - View Labels: Label each view according to patient-to-detector orientation, as well as the time post last swallow (e.g. **Detector 1:** ANT 5min, **Detector 2:** POST 5min).
 - **Orientation:** Head Out
- After the *STATIC* **4hr** image, show the Nuclear Medicine Physician to see if any further imaging is required.

Sources of Error:

- Vomiting after meal ingestion
- Poor labelling
- A nonstandard meal
- A marked variation in the environment, such as noise, lighting, or temperature during imaging. Emotional fluctuations, such as fear of the medical environment, anxieties about results, anger after a long wait for the study to begin

Suggested Standard Meal For Gastro-oesophageal Scintigraphy

- Jungle Oatso Easy 50g satchet
- Protifar 14g powder
- Sugar or Replace 10g *
- Boiling water 180 ml
- Add boiling water to the dry ingredients
- Stir briskly
- Add and mix 20-30 MBq of Tc99m-Tin colloid
- *NOTE
- Replace is tasteless but provides the same amount of carbohydrate as sugar does. In order to adjust for individual patient sweet taste preference, the total (10g) sugar or Replace should always remain constant, but the proportion of each can be changed. For example:
- 5 g sugar + 5 g Replace
 - OR
- 10 g sugar + 0 g Replace

[figure not shown]
OR

• 0 g sugar + 10 g Replace

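### The plan provides no masking for whoever reads the day 1 scintigraphy, which supplies one of the two primary outcome components

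*Combined protocol and SAP*

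**What the plan says.** Under Methods, Trial Design, three statements settle who knows the allocation. On the patient: "the patient will remain blinded to the type of stent placed". On the investigators: "Although the authors will not be blinded to the stent type", because the two stents can be told apart at endoscopy. On the follow-up assessor: "the Clinical Coordinator who will be doing the follow-up will be blinded to this". The Interventions section repeats the patient's masking and adds nobody else.

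The Follow-up section sets the scope of the coordinator's role: "Telephonic follow-up of these patients will be done by the Clinical Coordinator". The calls are at weeks 1, 2, 4 and 8.

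Scintigraphy has primary status. The primary objective includes "objectively measured rates of volume GOR using scintigraphy". The Primary Outcome Measure section says: "The primary outcome will be patient-reported rates of symptomatic volume GOR and objectively measured volume GOR in both study groups". It then gives the source of the second part: "GOR will also be objectively measured on day 1 post stent insertion using scintigraphy".

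Appendix 3 is the Nuclear Medicine Department's standard protocol. It covers the meal, the tracer, positioning and image acquisition. The only role it names as looking at the images appears after the 4-hour image, where the instruction is to "show the Nuclear Medicine Physician to see if any further imaging is required".

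**The concern.** The plan deals with assessor masking for the questionnaire and has no counterpart for the scan. The two components are therefore unequally protected, although both are primary.

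The background section describes symptom reporting as subjective and presents scintigraphy as a way to confirm and quantify reflux objectively. A secondary objective also uses the scan as the comparator for GerdQ. Its worth in both roles depends on the reading being independent of the arm. If the reader knows that a valve is in place, expectation can enter wherever the reading leaves room for judgement. A difference between arms could then partly reflect the reader. This would weaken the scan as independent confirmation, though it would not make it worthless.

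**Working it through.** **Step 1. Who is covered.** The statements on masking, set against the outcome each one protects:

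| Role | Masking in the plan | Outcome affected |
|---|---|---|
| Patient | Masked (Trial Design, Interventions) | GerdQ, dysphagia, pain, cough |
| Clinical Coordinator | Masked (Trial Design) | Telephone assessments, weeks 1, 2, 4 and 8 |
| Investigators | Not masked (Trial Design) | Insertion; no scan reading is assigned to them |
| Scintigraphy reader | Not mentioned | Day 1 reflux, a primary component |

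**Step 2. Can stent type reach the reader?** The scan takes place the day after stenting, in the same hospital, before discharge. The operators know the stent type. No section describes a coded request, or says that the stent type or endoscopy report is withheld. Equally, no section says that either accompanies the request. The route is open but not shown to be used.

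**Step 3. Can judgement enter the reading?** The Data Collection list calls the scan variable quantitative, and Appendix 3 standardises the meal, requires the same position and camera distance throughout, and sets 60-second views with images at 0, 1, 2, 3 and 4 hours. But Appendix 3 gives no region of interest, threshold or rule for what counts as reflux. Appendix 7 lists clearance, reflux, secondary clearance and gastric emptying as fields without saying how each is scored. Imaging beyond 4 hours is discretionary. There is room for judgement, of unstated extent.

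**Step 4. The plan's own figure.** Inputs from the Sample Size section: difference 2, SD 3, alpha 5%, power 80%. Per arm, n = 2 × (1.960 + 0.842)² × 3² / 2² = 35.3, rounded up to 36, or 72 in total. This matches the plan (two-sided, normal approximation). It rests on GerdQ means alone, so masking the scan reader does not alter it.

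**Step 5. What a reader shift could do.** The documents give no reflux rate for the scan and no estimate of reader bias, so both are assumed here. Take 36 per arm, true reflux of 50% in both arms, and a reader who reports a lower proportion in the anti-reflux arm. Summing the exact binomial probabilities of all tables with p < 0.05 (two-sided) gives:

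| Proportion read in anti-reflux arm | Chi-square, uncorrected | With continuity correction |
|---|---|---|
| 50% (no shift) | 4.5% | 2.5% |
| 45% | 6.5% | 3.8% |
| 40% | 12.9% | 8.2% |
| 35% | 24.3% | 17.0% |

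The plan names no test for this comparison, so both versions are shown.

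If the measure is analysed as continuous, a shift of b standard deviations moves the test statistic by b / √(2/36). For b = 0.1, 0.2 and 0.3 that is 0.42, 0.85 and 1.27, and the chance of p < 0.05 rises from 5% to about 7%, 14% and 25%.

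**The case against.** The strongest reply is that this is silence and not a fault. A reader might infer from the list of masked roles that the scan reader is unmasked. The documents do not support that. Only the authors are said to be unblinded, and the reason given is that the stents look different at endoscopy. Insertions are done by two consultants of the Upper Gastrointestinal Surgery Unit, while the scan protocol comes from another department. Nothing says that an author reads scans or that allocation is sent to Nuclear Medicine, and the trial registry is open only to investigators. All of this stands: the gap is a missing safeguard, and no actual unmasking is shown.

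A second reply is that the scan is quantitative and standardised. This stands in part. What is standardised is acquisition; the scoring of reflux is not defined. The instruction on further imaging concerns extra images and does not itself show how reflux is scored.

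A third reply is that the error rates are built on invented shifts, assume a binary reading although one section calls the variable quantitative, and fall when a continuity correction is used. That is correct. They show sensitivity and are not an estimate for this trial.

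Finally, the sample size rests on GerdQ, which a masked patient reports to a masked coordinator. That component is protected at the telephone calls. This limits the weight of the point but does not remove it, because scintigraphy is still named as primary.

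**Conclusion.** The point holds in this form: the plan masks the patient and the telephone coordinator and provides no masking for whoever reads or quantifies the day 1 scan, which is one of two primary components. It is more than a missing detail. Run as written, the scan passes through a hospital department with nothing to keep stent type from the reader, no stated rule for scoring reflux, and discretion over further imaging.

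The size of any bias is unknown and may be nil if masked reading already happens in practice. Under the assumed 50% rate and shifts of 5 to 15 percentage points, the false-positive rate for this component would be 6.5% to 24.3% uncorrected, or 3.8% to 17.0% corrected. These figures depend wholly on the assumed rate, shift and test. The GerdQ component and the sample size of 72 are not affected. The change should be made before scans are read.

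**What to change.** In Trial Design, add the person who reads or quantifies the scintigraphy to the list of masked roles. In both Trial Design and Appendix 3, state that:

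- scans are requested and read under the trial number only, without the stent type or the endoscopy report;
- all scintigraphy variables, and any decision on imaging beyond the 4-hour image, are recorded before allocation is disclosed to the reader.

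Masking does not require the same reader throughout the planned 36 months, so that need not be specified.

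The cost is a coded request form and minor administration. No extra reader, scan, visit or patient is needed. If masked reading is already intended, the change only writes it down, which also serves the plan's commitment to the CONSORT 2010 checklist.

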- Once deployed, the distal end of the stent must have crossed the OGJ junction and be lying within the proximal stomach

Exclusion Criteria:

- Patient declining or unable to give informed consent, including inability to speak or understand either English, Afrikaans or isiXhosa.
- Patient unable to comply with the follow-up protocol of the trial (e.g. does not have a contactable telephone number)
- Oesophageal cancers selected for curative treatment or irresectable oesophageal cancers selected for palliative chemoradiation, but not requiring oesophageal stenting
- Benign oesophageal pathology or extrinsic compression of the oesophagus from another cause
- Patients with oesophageal cancers where the stent does not cross the OGJ
- Pregnant patients
- Patient performance status precluding any intervention or sedation

Setting and Location of Trial

This trial will take place at the Upper Gastrointestinal Surgery Unit at Groote Schuur Hospital (GSH). All stent insertions for the trial will be performed by either of the two full-time consultants working in the Upper Gastrointestinal Surgery Unit at GSH. Palliative oesophageal stenting is performed in the endoscopy suite in E23 under conscious sedation. After appropriate post-procedural observation in the unit, the patient will be admitted to the hospital for overnight observation and if deemed well enough, will be discharged home the following day after the scintigraphy.

Interventions

Patients considered eligible for the trial will be enrolled after obtaining informed consent. Oesophageal stenting will be performed according to standard practices at the GSH endoscopy suite using video endoscopy (standard gastroscope) and fluoroscopy. Patients will be appropriately sedated for the procedure, provided with supplemental oxygen and a diagnostic upper gastrointestinal endoscopy will then be performed to confirm the site and length of the histologically confirmed oesophageal cancer. Randomisation will then occur only if stenting is required which will result in OGJ overlap. Regardless of which type of stent the patient receives, all enrolled participants will be prescribed a twice daily dose of a proton pump inhibitor post the procedure, which is continued indefinitely as per the current standard of care at GSH.

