Randomisation will be done using opaque, sealed envelopes with computer-generated random numbers in blocks of 20 (10:10). Patients will be randomised to either receive a conventional oesophageal stent or an anti-reflux oesophageal stent. Other than the anti-reflux mechanism, all other parameters of the two stents will be the same – both stents will be fully covered Nitinol self-expanding metal stents designed for deployment in the oesophagus (conventional stent: Taewoong Niti-S Esophageal Covered Stent, distributor: First Medical Company [Global Medical Device Nomenclature Code 61751] and anti-reflux stent: Taewoong Niti-S Esophageal Covered AR Stent, distributor: First Medical Company [Global Medical Device Nomenclature Code 61751] and anti-reflux stent: Taewoong Niti-S Esophageal Covered AR Stent, distributor: First Medical Company [Global Medical Device Nomenclature Code 48136]). Both stent types come in a standard length of 120mm. Both of these stents are available and currently form part of the standard of care at GSH, although the stent selection is determined by stent availability and endoscopist preference – the conventional stent is generally favoured. Both are approved by SAHPRA as part of First Medical's list of approved devices they can import into and distributed in South Africa.

The technique of stent deployment will also be the same for both anti-reflux and conventional stents. Stent position and deployment success will be confirmed after stent placement, using water-soluble contrast injected through the stent under fluoroscopy – this will confirm the distal stent position crossing the OGJ. The patient will remain unaware of which type of stent they are receiving. The progress of the trial will be documented according to the CONSORT 2010 flow diagram²².

Follow-up

Technical success of the stent insertion will be confirmed using fluoroscopy immediately after insertion. Any insertion-related complications will be documented. All patients will be appropriately observed in the gastrointestinal unit after the procedure and then admitted to the ward for overnight observation. They will undergo scintigraphy the following day (day 1 post the procedure) and then if deemed well enough will be either discharged home or referred back to their referring hospital. The follow-up period will subsequently continue for a total of 8 weeks.

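### A mandatory inclusion criterion can be verified only after randomisation, conflicts with the protocol's own pre-randomisation check, and no analysis set covers patients who fail it (minor)

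*Combined protocol and SAP*

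**What the plan says.** The heading of the inclusion list (Participants) makes every criterion mandatory. One criterion is: "Once deployed, the distal end of the stent must have crossed the OGJ junction and be lying within the proximal stomach". An exclusion criterion mirrors it without saying when it is judged: "Patients with oesophageal cancers where the stent does not cross the OGJ".

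The order of events is given in three places:

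- Trial Design: "Randomisation to an anti-reflux stent versus a conventional stent will be done prior to stent placement".
- Interventions, after the diagnostic endoscopy: "Randomisation will then occur only if stenting is required which will result in OGJ overlap".
- Interventions, after deployment: "Stent position and deployment success will be confirmed after stent placement", by contrast under fluoroscopy, and "this will confirm the distal stent position crossing the OGJ".

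Trial Design also says that the investigators are not blinded to stent type, because the two stents are easily told apart at endoscopy.

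Other text bears on what happens to a patient whose stent does not cross. Appendix 7, item 4, lists incorrect placement among the immediate insertion complications. Secondary Outcome Measures includes immediate technical success. Follow-up describes observation, admission and day-1 scintigraphy for all patients, with no exception for misplaced stents. Interventions promises a CONSORT 2010 flow diagram. The Statistical Analysis and Sample Size sections name no analysis population and give no rule for keeping, excluding or replacing a randomised patient.

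**The concern.** Eligibility should be settled by facts known before allocation. Here the overlap requirement appears twice, as a forecast before randomisation and as a fact after deployment, and only the second stands in the list of mandatory criteria. A patient can pass the forecast, be randomised, and then fail the criterion because of where the allocated device came to rest.

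If such patients are dropped, the arms compared are no longer the arms randomised. The judgement could be made knowing the stent type, since the investigators are unblinded; the documents do not say who decides that the stent has crossed. Position is also plausibly related to the outcome, and in either direction. The introduction attributes reflux to the stent crossing the lower sphincter, so non-crossers might reflux less. They might instead score higher if still obstructed, because GerdQ item 2 (Appendix 2) counts food or liquid coming up to the throat; that second route is inference.

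Technical success is exposed in the same way. If a short placement makes the patient ineligible, insertion failures leave the denominator of the outcome meant to count them.

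**Working it through.** **The passages side by side**

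| Step | Section | What is known about overlap |
|---|---|---|
| Diagnostic endoscopy | Interventions | Expected overlap |
| Randomisation | Trial Design; Interventions | Expected overlap only |
| Deployment | Interventions | Allocated stent is placed |
| Contrast fluoroscopy | Interventions | Actual position |
| Criterion satisfied or not | Inclusion Criteria | Needs actual position |

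The criterion cannot be checked at the time of randomisation.

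**The plan's own figure**

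Sample Size gives means of 9 and 7 (difference 2), SD 3, alpha 5% and power 80%. With a two-sided test, n per arm = 2 × (1.960 + 0.842)² × 3² / 2² = 35.3, rounded up to 36, total 72. This matches the stated size. A one-sided test would give 28 per arm, so the plan's 5% is two-sided. Power at 36 per arm is 80.7% by the normal formula and 79.7% by the t-test. The t-test is used below.

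**Assumed inputs**

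The documents give no rate of non-crossing, no GerdQ gap and no imbalance between arms. I assume that k = 1, 2 or 4 of 36 are excluded, and that excluded and retained patients differ by d = 1, 2 or 3 points, sign unknown.

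**Type I error if patients are excluded from one arm only**

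Shift in that arm's mean = (k/36) × d. For example, k = 2 and d = 3 gives 2/36 × 3 = 0.167. The standard error is 3 × √(1/34 + 1/36) = 0.717, so the noncentrality is 0.167/0.717 = 0.232, and the two-sided rejection rate at no true difference is 5.6%.

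| d | k = 1 | k = 2 | k = 4 |
|---|---|---|---|
| 1 point | 0.03; 5.0% | 0.06; 5.1% | 0.11; 5.3% |
| 2 points | 0.06; 5.1% | 0.11; 5.3% | 0.22; 6.0% |
| 3 points | 0.08; 5.2% | 0.17; 5.6% | 0.33; 7.4% |

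(Each cell: shift in points; two-sided type I error.)

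With 4 excluded from one arm and 2 from the other at d = 3, the shift is (4 − 2)/36 × 3 = 0.167 and type I error is 5.6%. Equal exclusions with equal gaps leave it at 5.0%.

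**Power, same number affected in each arm**

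- Excluded and not replaced, difference 2: 35, 34 or 32 per arm gives 78.5%, 77.3% or 74.7%.
- Retained, with no stent benefit at all in the misplaced (assumed worst case): difference 2 × (1 − k/36) = 1.94, 1.89 or 1.78; power at 36 per arm is 77.4%, 75.0% or 69.8%.

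In this worst case, keeping the patients costs more power than excluding them.

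**The case against.** The strongest reply is that overlap is in practice decided before allocation. The Interventions section is the only text that says when overlap controls entry, and it places the decision at the diagnostic endoscopy. On this reading the inclusion bullet says where the stent should end up, the endoscopic check screens for it, and fluoroscopy confirms it. The data sheet then treats misplacement as a complication in a trial participant, and the follow-up text makes no exception. Imbalance between arms should also be small: the stents are stated to match apart from the anti-reflux mechanism, "The technique of stent deployment will also be the same for both anti-reflux and conventional stents", and two consultants place them all.

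Most of this stands. It makes failures few and a large imbalance unlikely, and it suggests that misplaced patients remain in the trial. It does not remove the conflict, because the mandatory criterion still turns on the deployed position, and recording or following a patient does not say whether that patient is analysed. The flow diagram would show an exclusion but would not prevent one.

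Three stronger readings are tempting, and the documents support none of them:

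- A reader might infer that the trial will remove non-crossers. No section instructs this.
- A reader might infer a real inflation of type I error, or a bias favouring one stent. The 7.4% figure needs 4 of 36 lost from one arm, none from the other, and a gap larger than the planned effect; the direction is unknown.
- A reader might infer that any exclusion leaves the trial short of its 72. That assumes no replacement, on which the documents are silent.

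The missing analysis population is also a wider gap than this one criterion. Here it matters because a stated eligibility rule, taken literally, supplies the exclusion.

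**Conclusion.** The point holds as a minor one. The inclusion wording and the pre-randomisation check are different tests at different times, and the protocol does not reconcile them. Read literally, the criterion permits exclusion after allocation on how the allocated device deployed, and nothing in the analysis text prevents it.

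No size can be derived from the documents. Under the assumed inputs, type I error stays at or below 5.6% when 1 or 2 patients leave one arm, for gaps up to 3 points, and reaches 6.0% or more only when 4 leave one arm and none the other with a gap of at least 2 points. The reason to act is to protect the randomised comparison, at almost no cost; the power figures do not argue for it.

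**What to change.** 1. Reword the inclusion criterion as a judgement made before randomisation, in line with the check already in Interventions. For example: *At the pre-randomisation endoscopy, the planned stent position crosses the OGJ with its distal end in the proximal stomach.* Word the mirror exclusion the same way, on planned position.
2. Add to Statistical Analysis: *All randomised patients are followed and analysed in the arm to which they were allocated.* Keep misplacement as the insertion complication already on the data sheet.
3. State that technical success is reported with all randomised patients as the denominator.

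A sensitivity analysis restricted to patients with confirmed crossing is optional.

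The cost is two lines of eligibility wording, one sentence on the analysis set and one denominator. The downside is dilution: if 4 of 36 in each arm were misplaced and had no stent benefit, the difference would be 1.78 points and power 69.8%, against 74.7% if they were excluded and not replaced. Interim analyses are planned at 12 and 24 months, so the choice should be written down before any outcome data are examined.
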